## 8. Statistical Considerations

This is an open label, phase II clinical trial to evaluate the efficacy of eltrombopag in combination with decitabine as a frontline therapy in patients with Intermediate-2 or High-Risk Myelodysplastic Syndrome (MDS). A total of 40 patients will be accrued from M.D. Anderson Cancer Center (MDACC), at a rate of 2-3 patients per month.

The primary endpoint is the overall response rate (ORR) based on the IWG-2006 criteria, which includes complete remission (CR), partial remission (PR), and hematologic improvement (HI). Patients' overall response will be assessed during the first four 28-day cycles of treatment. Patients who drop off the study early due to treatment-related toxicities will be counted as treatment failures (i.e., non-responders).

The method of Thall, Simon and Estey [1995] will be used for futility and toxicity monitoring for this study. The target overall response rate is 60% and the following futility stopping rule will be applied in cohort size of 10, starting from the 10th patient:  $\text{prob}\{p(\text{ORR}) < 0.6\} > 0.95$ , where  $p(\text{ORR})$  denotes the overall response rate. That is, the trial will be stopped early due to futility, if during the study we determine that there is more than 95% chance that the ORR is less than 60%. Assuming that the prior distribution of  $p(\text{ORR})$  is beta (1.2, 0.8), the stopping boundaries corresponding to this futility monitoring rule are shown below in Table 1. The operating characteristics (OCs) for this futility stopping rule are summarized in Table 2. The design software Multic Lean Desktop (version 1.2.0) developed by the Department of Biostatistics at M. D. Anderson Cancer Center (MDACC) was used to generate the futility stopping boundaries and the

OC table. In order to utilize the software for the design, a highly informative beta (600, 400) prior was assumed to approximate the target 60% overall response rate.

Table 1. Futility stopping boundaries in cohort size of 10.

Number of patients	Stop the trial if there are this many patients achieving overall response
10	0-3
20	0-8
30	0-13

Table 2. Operating characteristics for futility monitoring in cohort size of 10 (max sample size = 40).

True ORR	Prob(stop the trial early due to futility)	Average sample size
0.3	0.971	14.8
0.4	0.775	22.0
0.5	0.391	31.3
0.6	0.105	37.5
0.7	0.015	39.6

Toxicity monitoring will be conducted in cohort size of 5, starting from the 5th patient. Denote the probability of toxicity by  $p(T)$ , where toxicity is defined as any grade 3-4 clinically relevant non-hematologic toxicity or a serious adverse event that is felt to be drug related (Common Terminology Criteria for Adverse Events CTCAE version 4.0). We assume as a priori,  $p(T) \sim \text{beta}(0.6, 1.4)$ . The trial will be stopped if  $\Pr(p(T) > 0.30 | \text{data}) > 0.90$ . That is, we will stop the trial for new patient enrollment if at any time during the study we determine that there is more than 90% chance that the toxicity rate is more than 30%. Stopping boundaries corresponding to this toxicity monitoring rule are shown in Table 3 below. The operating characteristics for toxicity monitoring are summarized in Table 4. Again, Multc Lean Desktop (version 1.2.0) was used to generate the toxicity stopping boundaries and the OC table and a highly informative beta (300,700) prior was assumed to approximate the fixed 30% toxicity rate.

Table 3. Toxicity stopping boundaries in cohort size of 5.

Number of patients	Stop the trial if there are this many patients having toxicities
5	4-5
10	6-10
15	8-15
20	9-20
25	11-25
30	13-30
35	15-35

Table 4. Operating characteristics for toxicity monitoring in cohort size of 5 (max sample size = 40).

True toxicity rate	Prob(stop the trial early)	Average sample size
0.10	0.0006	40.0
0.20	0.020	39.4
0.30	0.186	35.8
0.40	0.583	26.8
0.50	0.905	17.3

The PI and the study statistician will review the efficacy and toxicity data quarterly in order to determine whether the stopping boundaries have been crossed.

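### Toxicity boundaries are tabulated for every fifth patient, but the only stated step for checking them is a quarterly review, by which time 6 to 9 patients have enrolled; the two must be reconciled

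*Combined protocol and SAP*

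**What the plan says.** All of this stands in section 8, Statistical Considerations, of the combined protocol and SAP.

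- **Schedule of looks.** "Toxicity monitoring will be conducted in cohort size of 5", beginning with the fifth patient. Table 3 has rows for 5, 10, 15, 20, 25, 30 and 35 patients and no others. Table 4 is labelled for cohorts of five with a maximum of 40 patients.
- **Criterion.** Enrolment stops when the posterior shows "more than 90% chance that the toxicity rate is more than 30" percent, under a beta(0.6, 1.4) prior. In the software "a highly informative beta (300,700) prior was assumed to approximate the fixed 30% toxicity rate".
- **Intent on timing.** "we will stop the trial for new patient enrollment if at any time during the study we determine" that the criterion is met.
- **Process.** The PI and the study statistician "will review the efficacy and toxicity data quarterly in order to determine whether the stopping boundaries have been crossed".
- **Accrual.** Forty patients "at a rate of 2-3 patients per month".

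No section describes a review triggered by the fifth patient, a pause in accrual at a cohort boundary, or a window for evaluating toxicity.

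**The concern.** A cohort of five fills in less than a quarter at either end of the accrual range, since 3 × 2 = 6 and 3 × 3 = 9. If the quarterly meeting is the occasion for deciding, a boundary can be met and enrolment can continue until the next meeting. The reviewers would also usually hold data on a number of patients for which Table 3 has no entry, and the plan does not say whether they should look back to the last tabulated row, check every row passed since the last meeting, or recompute the posterior. This would occur even if every toxicity were known on the day it happened.

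At stake is the average sample size column of Table 4 when toxicity is high. Those figures tell a reviewing committee how many patients would be exposed before the rule halts enrolment, and this is the only study-level toxicity stopping rule in the plan.

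**Working it through.** **Inputs.** All are from section 8: prior beta(0.6, 1.4); stop if Pr(p > 0.30 | data) > 0.90; looks at n = 5, 10, ..., 35; maximum 40; accrual 2 to 3 per month; review every 3 months.

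**Step 1: reproduce Table 3.** After x toxicities in n patients the posterior is beta(0.6 + x, 1.4 + n − x). The smallest x with Pr(p > 0.30) > 0.90 is 4, 6, 8, 9, 11, 13, 15 at n = 5, 10, ..., 35. This equals Table 3, whether 0.30 is fixed or replaced by beta(300, 700).

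**Step 2: reproduce Table 4.** An exact binomial recursion gives s(n), the probability of first crossing at look n. The stop probability is Σ s(n), and average N = Σ n·s(n) + 40·(1 − Σ s(n)). Stop probability / average N comes out as 0.0006 / 40.0, 0.021 / 39.4, 0.186 / 35.8, 0.583 / 26.8 and 0.905 / 17.3 at true rates 0.10 to 0.50. This agrees with Table 4, apart from 0.021 against the printed 0.020 at 0.20. Table 4 therefore assumes that enrolment stops exactly at the five-patient look.

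**Step 3: where quarterly reviews fall.** With even accrual and the first review three months after the start, reviews fall at 6, 12, 18, 24, 30, 36 (2 per month) or at 9, 18, 27, 36 (3 per month). Only n = 30 at 2 per month matches a Table 3 row.

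| Boundary met at n | 5 | 10 | 15 | 20 | 25 | 30 | 35 |
|---|---|---|---|---|---|---|---|
| s(n), true rate 0.50 | 0.1875 | 0.2197 | 0.1516 | 0.2115 | 0.0656 | 0.0407 | 0.0279 |
| Enrolled at next review, 2/month | 6 | 12 | 18 | 24 | 30 | 30 | 36 |
| Enrolled at next review, 3/month | 9 | 18 | 18 | 27 | 27 | 36 | 36 |

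The excess at a single crossing is 0 to 5 patients at 2 per month and 1 to 8 at 3 per month.

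**Step 4: Table 3 boundaries acted on at the next quarterly review.** Outcomes are taken as known at once, and every boundary passed is checked retrospectively. Replace n in the average by the number enrolled. At true rate 0.50 the final term is 40 × 0.0954 = 3.82, and:

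- five-patient looks: 0.94 + 2.20 + 2.27 + 4.23 + 1.64 + 1.22 + 0.98 + 3.82 = 17.3
- 2 per month: 1.13 + 2.64 + 2.73 + 5.08 + 1.97 + 1.22 + 1.00 + 3.82 = 19.6
- 3 per month: 1.69 + 3.95 + 2.73 + 5.71 + 1.77 + 1.47 + 1.00 + 3.82 = 22.1

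**Step 5: posterior rule recalculated at the actual quarterly n.** The minimum counts become 4, 6, 9, 11, 13, 15 at n = 6, 12, 18, 24, 30, 36, and 5, 9, 12, 15 at n = 9, 18, 27, 36. The same recursion is then run on those looks.

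| True rate | Table 4 average N | Step 4, 2 to 3/month | Step 5, 2 to 3/month |
|---|---|---|---|
| 0.30 | 35.8 | 36.3 to 36.7 | 34.7 to 35.9 |
| 0.40 | 26.8 | 28.4 to 29.9 | 25.5 to 27.6 |
| 0.50 | 17.3 | 19.6 to 22.1 | 16.1 to 18.4 |

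**Step 6: stop probabilities.** In step 4 they equal Table 4, but only because every passed boundary is checked. If each review checks only the latest completed multiple of five, at 3 per month they fall to 0.148 (from 0.186) at true rate 0.30, 0.534 (from 0.583) at 0.40 and 0.887 (from 0.905) at 0.50. In step 5 the stop probability at 0.50 is 0.920 (2 per month) or 0.911 (3 per month), against 0.905.

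**The case against.** The strongest reply is that five-patient monitoring is itself stated as a requirement, that the rule is meant to operate "if at any time during the study we determine that there is more than 90% chance", and that the quarterly meeting may be a routine addition. Nothing says that monitoring is only quarterly. This stands as a possible reading. It does not settle the matter, because stopping depends on a determination and the quarterly review is the only stated occasion for making one.

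A second reply is that the rule is the posterior criterion and Table 3 merely lists its consequences. Step 5 bears this out: recalculated at the quarterly numbers, the rule roughly delivers Table 4, and at 2 per month it stops slightly earlier on average. What remains is that the plan neither says that this will be done nor gives the boundaries.

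A third reply is that safety oversight continues between meetings. The PI evaluates serious adverse events within 48 hours (section 4.5.3), they go to the study supporter within 24 hours (section 6.2.2.3), and either the supporter or the investigator may terminate the study (section 7.4). This lowers the risk of an unnoticed problem. It is not a study-level stopping rule, though, and the monitored toxicity also counts grade 3-4 clinically relevant non-hematologic events that need not be serious.

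A reader might infer that the five-patient looks cannot take place on time, or that Table 4's early stopping is lost. The documents support neither. The first ignores the stated five-patient monitoring, and the second holds only under the convention of step 4.

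**Conclusion.** The review process and the boundary tables do not match as written and need to be reconciled. The size depends on a convention that the plan leaves open. If Table 3 is acted on only at the next quarterly review, the average excess is about 2.3 to 4.8 patients at a true rate of 0.50 and about 1.6 to 3.0 at 0.40. At 0.30 or below it is at most about one. If the posterior is recalculated at the actual number, there is little or no excess. The case of 18 enrolled after a crossing at patient 10 is the extreme, not the typical result.

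These figures assume even accrual, a first review at three months and immediate outcomes. Under an assumed 28-day toxicity lag and a random review date, simulation at true rate 0.50 gives average N (2 to 3 per month) of 18.2 to 19.1 for looks triggered by each fifth patient, 21.3 to 23.4 for quarterly checks of Table 3, and 18.7 to 21.5 for quarterly recalculation. Triggered looks therefore help, but they do not fully restore Table 4.

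The change is worth making because it is cheap and because the excess, where it arises, falls when toxicity is high. It is not a flaw that invalidates the design.

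**What to change.** Preferred: in section 8, state that the PI and the study statistician review toxicity when patients 5, 10, 15, 20, 25, 30 and 35 are reached and futility when patients 10, 20 and 30 are reached, with the quarterly review kept as an additional minimum. Tables 1 to 4 then stand unchanged.

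Alternative, if calendar reviews are kept: state that the posterior rule is applied at the number of patients actually available at each review, give boundaries for those numbers (step 5 shows them for even accrual at 2 and 3 per month), and restate Table 4 on that schedule.

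Either way, state the toxicity evaluation window and whether accrual continues while a cohort is being evaluated.

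The cost of the preferred version is one sentence and seven short reviews by people already assigned, against four to six quarterly reviews before the fortieth patient. The three futility looks coincide with toxicity looks. The stopping criterion and sample size do not change. Any delay in observing outcomes would still leave average enrolment somewhat above Table 4.

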## 8.1 Analysis Plan

The primary endpoint is overall response rate (ORR). The ORR will be estimated along with the exact 95% confidence interval. Secondary endpoints include incidence of dose reductions and delays of decitabine therapy, hemorrhagic events (defined as Grade 3 or 4 hemorrhagic events on CTCAE v 4.0), platelet and RBC transfusion independence per IWG-2006 criteria, transformation from MDS to AML, Incidence and severity of bone marrow fibrosis. Descriptive statistics will be used to summarize all secondary endpoints. The incidence rates of binary secondary endpoints will be estimated, along with the exact 95% confidence intervals.

The probabilities of time-to-event outcomes (such as time to transformation from MDS to AML and time to developing BM fibrosis) will be estimated using the method of

Kaplan and Meier. Log-rank tests will be used to compare the time-to-event outcomes among subgroups of patients.

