### **1.2 Secondary Objectives**

The secondary objectives of the study are:

- To evaluate the safety and tolerability of the combination of eltrombopag and decitabine. Safety will be assessed by the overall incidence and severity of all study-treatment related adverse events per CTCAE v 4.0
- To evaluate the incidence of dose reductions and delays of decitabine therapy
- To evaluate the effect of eltrombopag on medically significant hemorrhagic events (defined as Grade 3 or 4 hemorrhagic events on CTCAE v 4.0)
- To evaluate the effect of eltrombopag on platelet and RBC transfusion independence per IWG-2006 criteria
- Incidence of transformation to AML per FAB criteria (>30% blasts) during treatment period and follow-up
- Incidence and severity of bone marrow fibrosis during treatment period and follow-up
- To examine the relationship between clinical response with ferritin level and other markers of iron burden at study start

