### **4.2. Study Duration**

4.2.1. All subjects must complete a screening visit, day 1 visits for each new cycle, an end of treatment visit and whenever possible, an end of study safety visit 28 days after the last dose of eltrombopag.

4.2.2. Treatment will continue until discontinuation due to relapse, unacceptable toxicity, or disease progression as defined by the IWG 2006 criteria for MDS. This includes:

- clinically significant progressive disease at any time, or

- a lack of clinical benefit after 4 cycles of treatment at the highest dose of study medication, or
- Possibility of undergoing allogeneic stem cell transplantation
- discontinuation of study drug for more than 6 weeks, or
- intercurrent illness that prevents further administration of treatment, or
- unacceptable adverse event(s), or
- patient decision for study withdrawal, or
- general or specific changes in the patient's condition that render the patient unacceptable for further treatment in the judgement of the investigator

4.2.3. Study cycles will be administered every 28 days  $\pm$  5 days or upon resolution of any clinically significant study drug related AE to grade 0-1, whichever occurs first. If a subsequent cycle is delayed due to adverse events related to decitabine, or if it is considered in the best interest of the patient to delay administration of decitabine (e.g. because of concern for an infection), administration of the eltrombopag may continue as planned.

4.2.4. Administration of subsequent cycles should be administered when neutrophils recover to  $\geq 1 \times 10^9/L$  and platelets to  $\geq 30 \times 10^9/L$  or to baseline levels prior to the start of the last cycle of therapy. Patients with residual disease may start the next cycle with neutrophil and/or platelet counts lower than these if judged to be in the best interest of the patient to start the next cycle. The decision to treat should be documented in the patient's medical record.

4.2.5. Patients may remain on study for up to 12 cycles if the patient demonstrates clinical benefit and no excessive toxicity (i.e. no clinically significant study-drug related grade  $\geq 3$  toxicity). Patients who are experiencing clinical benefit and have not experienced excessive toxicity may be eligible to continue therapy after discussion with the PI and the discussion documented in the patient's medical record.

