## 5.2 On-Study Procedures

PROCEDURES	Pre-Study Screen o	Cycle 1 Day 1	Cycle 1 Day 8 (+/- 2 days)	Cycle 1 Day 15 (+/- 2 days)	Cycle 1 Day 22 (+/- 2 days)	Day 1 Cycle 2 onwards (+/- 5 days)	End of Treatment Visit (+/- 5 days)	Safety Visit 28 days after last dose (+/- 28 days)
Informed Consent	X							
Eligibility	X	X						
Medical History	X							
Patient Weight	X							
Vital Signs	X	X	X	X	X	X	X	X
Physical Exam and Performance Status	X	X				X	X	X
Concomitant Medications	X	X	X	X	X	X	X	X
Transfusion and Supportive Care Assessment	X	X	X	X	X	X	X	X
CBC with differential	X*	X	X	X	X	X 	X	X 
Blood Chemistries (AST, ALT, bilirubin)	X** a	X	X	X	X	X 	X	X
12-lead EKG	X a							
Bone marrow aspiration and/or biopsy	X					X 	X	
IPSS score & WHO disease classification	X					X 	X	
Pregnancy Test	X†							
Investigational Drug Dispense		X				X		
AE and SAE assessment	X	X	X	X	X	X	X	X
Optional: Correlative studies 	X							

oScreening must be performed within 4 weeks prior to study drug initiation / study start unless otherwise indicated

\*CBC with differential and blood chemistries including iron studies (sodium, potassium, BUN, creatinine, glucose, calcium, phosphate, magnesium, AST, ALT, total bilirubin, alkaline phosphate, uric acid, serum iron, transferrin, transferrin saturation, total iron binding capacity and ferritin) must be performed within 72 hours of Cycle 1 Day 1

^Serum iron, transferrin, transferrin saturation, total iron binding capacity and ferritin are required only on Cycle 1 Day 1 and do not need to be repeated

aEKG, including QTc intervals, at screening or baseline. A follow-up EKG will be performed if a subject experiences a clinically relevant abnormality.

†Within 7 days of Day 1 in females of child-bearing potential

Weekly CBC with differential and blood chemistries required until stable counts, and weekly x4 weeks after any change in eltrombopag dosing

Weekly CBC with differential should be performed weekly for the 4 weeks after discontinuation of eltrombopag

Bone marrow aspiration and/or biopsy with cytogenetics required for study entry, and every cycle for the first 4 cycles for primary outcome, and then every 3 cycles as clinically indicated. Cytogenetics do not need to be repeated if normal at study start.

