#### **Survival Endpoints:**

- Overall: death from any cause
- Event free: failure or death from any cause
- PFS: disease progression or death from MDS
- DFS: time to relapse
- Cause specific death: death related to MDS

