#### **6.2.3. Secondary Efficacy Endpoints**

The key secondary endpoints for this study are:

- To evaluate the safety and tolerability of the combination of eltrombopag and decitabine. Safety will be assessed by the overall incidence and severity of all study-treatment related adverse events per CTCAE v 4.0
- To evaluate the incidence of dose reductions and delays of decitabine therapy
- To evaluate the effect of eltrombopag on medically significant hemorrhagic events (defined as Grade 3 or 4 hemorrhagic events on CTCAE v 4.0)
- To evaluate the effect of eltrombopag on platelet and RBC transfusion independence per IWG-2006 criteria
  - o Platelet IWG-2006: A complete response is defined as a platelet count  $> 100 \times 10^9/L$ ; and a major response defined as an increase of platelet count by higher than  $30 \times 10^9/L$ .
  - o Durable platelet count: in which a hematologic improvement in platelets (HI-P) defined as either an increase  $\geq 30 \times 10^9/L$  from patients with a baseline platelet count  $\geq 20 \times 10^9/L$ , or an increase from  $< 20 \times 10^9/L$  to  $\geq 20 \times 10^9/L$  and by at least 100%, present for  $\geq 8$  weeks.
- Incidence of transformation to AML per FAB criteria ( $>30\%$  blasts) during treatment period and follow-up
- Incidence and severity of bone marrow fibrosis during treatment period and follow-up
- To examine the relationship between clinical response with ferritin level and other markers of iron burden at study start

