## 8.3. Analysis of Key Study Endpoints

The primary endpoint is overall response rate (ORR). The ORR will be evaluated along with the exact 95% confidence interval. Secondary endpoints include platelet response, durable platelet response, transformation to AML, incidence of bone marrow fibrosis, and time-to-event outcomes such as progression-free survival (PFS) and overall survival (OS). The probabilities of PFS and OS will be estimated using the method of Kaplan and Meier. The incidence rates of other binary secondary endpoints will be estimated, along with the exact 95% confidence intervals. Subjects that discontinue the study prior to having achieved a clinical response will be considered to have not had an event.

**Patients receiving growth factors other than eltrombopag (erythropoietin, GM-CSF or G-CSF) will not be considered in the HI analysis for the time periods specified in Section 4.5.3 Supportive Care Guidelines. Hemoglobin levels and platelet counts collected from patients that have received a transfusion within the last 7 days will not be considered in the analysis.**

Survival or times to failure and time to progression functions will be estimated using the Kaplan-Meier method. The two-sided log-rank test will be used to assess the differences of time to events between groups.

The total number of dose administrations, the average dose (mg), and the cumulative dose administered will be summarized by eltrombopag treatment group.

Blood chemistry and complete blood counts will be summarized by treatment group at each time point.

Additional exploratory analyses of the key study endpoints will be performed as deemed appropriate.

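### Section 8.1 uses Kaplan-Meier for the probability of AML transformation and marrow fibrosis without treating death as a competing event, so both would be slightly overstated

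*Combined protocol and SAP*

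**What the plan says.** Section 8.1 (Analysis Plan) says: "The probabilities of time-to-event outcomes (such as time to transformation from MDS to AML and time to developing BM fibrosis) will be estimated" by the Kaplan-Meier method, with log-rank tests among subgroups.

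The two outcomes are defined without reference to death. Section 1.2 has "Incidence of transformation to AML per FAB criteria (>30% blasts) during treatment period and follow-up", and Section 6.2.3 has "Incidence and severity of bone marrow fibrosis during treatment period and follow-up".

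Sections 8.1 and 8.3 also give a second analysis. In 8.1: "The incidence rates of binary secondary endpoints will be estimated, along with the exact 95% confidence intervals".

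Nothing in the plan says how a death before AML or fibrosis enters these curves. There is no competing-event rule, no censoring rule for such deaths and no cumulative-incidence estimator. Two places come near but do not settle it. The survival definitions in Section 6.2.1 cover overall, event-free, progression-free and disease-free survival and cause-specific death only. The sentence in 8.3 on subjects who discontinue concerns clinical response.

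**The concern.** A patient who dies free of AML can no longer transform. Kaplan-Meier with that death censored treats the patient as if still at risk and represented by those who remain. The result describes a hypothetical setting in which nobody dies first. Section 8.1 calls the quantity a probability, and readers will take it as the share of patients who develop AML or fibrosis. Read that way, it is biased upward.

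Both outcomes bear on safety: Section 2.3.2 discusses marrow fibrosis as a risk of eltrombopag. The report could also show a crude proportion and a higher curve for the same event, with no stated reason for the difference.

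The log-rank test is not at fault, since it is valid as a comparison of cause-specific hazards.

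**Working it through.** The plan states no expected probability for either outcome, so there is no figure of its own to reproduce.

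**Direction.** At each event time with r patients at risk, 1-KM rises by K/r, where K is the Kaplan-Meier curve that ignores deaths. The cumulative incidence (CIF) rises by S/r, where S is the proportion alive and event-free. After the first death without the event, K exceeds S. From the next event onward, 1-KM is therefore above the CIF.

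**Inputs from the documents**
- Median survival of 27 months with platelets below 100 × 10⁹/L (Section 2.1). It comes from a general primary-MDS series, not a higher-risk one, and is read here as all-cause.
- Horizon: "Patients may remain on study for up to 12 cycles if the patient demonstrates clinical benefit" (Section 4.2). Twelve 28-day cycles are 12 × 28 / 30.4375 = 11.04 months; four cycles are 3.68 months.
- N = 40 (Section 8).

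**Assumptions, not in the documents**
- Constant hazards.
- Median time to AML of 24 or 36 months.
- Median survival after AML of 3, 6 or 12 months.

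**Formulas.** Let ha, hd and hp be the monthly hazards of AML, of death without AML and of death after AML.
- 1-KM = 1 − exp(−ha·t)
- CIF = ha/(ha+hd) × [1 − exp(−(ha+hd)·t)]
- hd is solved so that all-cause survival at 27 months is 0.5: exp(−(ha+hd)·27) + ha/(hp−ha−hd) × [exp(−(ha+hd)·27) − exp(−hp·27)] = 0.5

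**One case in full.** AML median 24 and post-AML median 6 give ha = ln2/24 = 0.0289 and hd = ln2/97.7 = 0.0071. At 11.04 months, 1-KM = 1 − exp(−0.319) = 27.3%. CIF = 0.803 × [1 − exp(−0.397)] = 26.3%. The excess is 0.99 points.

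**All six cases**

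| AML median (mo) | Post-AML median (mo) | Solved median, death without AML (mo) | Excess at 3.68 mo (points) | Excess at 11.04 mo (points) | Excess at 12 mo (points) |
|---|---|---|---|---|---|
| 24 | 3 | 394.7 | 0.03 | 0.25 | 0.29 |
| 24 | 6 | 97.7 | 0.13 | 0.99 | 1.14 |
| 24 | 12 | 44.9 | 0.28 | 2.08 | 2.41 |
| 36 | 3 | 70.9 | 0.12 | 0.96 | 1.12 |
| 36 | 6 | 51.7 | 0.16 | 1.30 | 1.51 |
| 36 | 12 | 36.5 | 0.23 | 1.81 | 2.10 |

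At 11.04 months this is 1-10% relative to the CIF, or 0.1-0.8 of a patient in 40 (0.0025 × 40 to 0.0208 × 40).

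**Against sampling error.** In 5,000 simulated trials of 40 patients per case, censored at 11.04 months, the mean gap was 0.2-2.1 points. The 5th to 95th percentiles lay between 0 and about 4.3. The SD of the Aalen-Johansen estimate was 6.0-7.0 points.

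**Sensitivity.** If death without AML is simply given a median of 13.5, 27 or 54 months, the 12-month excess is 7.0, 3.9 or 2.0 points (AML median 24) and 5.1, 2.8 or 1.5 points (AML median 36). A separate calculation applied the 27-month median wholly to death without the event, with an assumed 12-month net event risk of 5-40%. It gave 0.7-5.1 points.

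**Fibrosis, illustration only.** Section 2.3.2 reports 7% with grade 2 fibrosis in ITP biopsies, which is not an MDS incidence. If the 12-month 1-KM were 7% (ha = −ln 0.93/12) and death without fibrosis had a median of 13.5, 27 or 54 months, the excess at 11.04 months would be 1.51, 0.83 or 0.43 points (0.2-0.6 of a patient in 40).

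**The case against.** The strongest reply is that this changes nothing that matters. The objectives are worded as incidences, and the plan already reports crude incidences with exact intervals, which do not carry this bias. The curves are descriptive displays in a single-arm trial of 40. In the main scenarios the excess is below sampling error. All of this stands, and it limits the weight of the point.

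The crude proportion is nevertheless not a full substitute. Accrual of 40 patients at 2-3 per month takes about 13-20 months (40/3 to 40/2), so follow-up may be unequal at the final analysis. The crude proportion would then miss events not yet observed, while 1-KM would overstate. Cumulative incidence handles both.

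A second reply is that censoring of deaths is nowhere stated. That is true. But the method is named, death is not part of either event, and censoring is what the method then does by default.

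A third reply is that the size is soft. This also stands. The AML and post-AML medians are assumptions. The lowest figure rests on an implausible 394.7-month median for death without AML, and the sensitivity range reaches about 7 points, similar to the sampling SD. The direction does not depend on these choices.

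**Conclusion.** The concern holds. For two secondary outcomes, Section 8.1 names an estimator that does not give the probability it is said to give once patients die without the event.

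Over the planned 12 cycles the likely excess for AML is small: 0.2-2.1 points under the illness-death assumptions above, and more only if death without AML is commoner than they imply. The excess grows with follow-up. Section 5.2 schedules marrows "every cycle for the first 4 cycles for primary outcome, and then every 3 cycles as clinically indicated", plus one at end of treatment, and gives no later schedule, so no figure is offered beyond 12 months.

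The finding is confined to these two curves. The correction is worth making because it removes the bias from censoring deaths at almost no cost, not because it would alter a conclusion.

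**What to change.** In Section 8.1, state that time to AML transformation and time to marrow fibrosis will be estimated by the cumulative incidence function (Aalen-Johansen), with death without the event as the competing event. Keep Kaplan-Meier for overall survival. The log-rank test may stay if described as comparing cause-specific hazards; Gray's test is optional. It would help to say also how allogeneic transplantation, a listed reason for stopping in Section 4.2.2, is handled in these analyses.

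A related wording point arises in Section 8.3: "The probabilities of PFS and OS will be estimated using the method of Kaplan and Meier". Section 6.2.1 defines "PFS: disease progression or death from MDS", so deaths from other causes fall outside that event and raise the same question. Section 8.3 should state how they are handled.

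The cost is a few lines of analysis text. Standard software does the estimation, and no new data or design change is needed.
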